To explore the treatment of optic
neuromyelitis with
electroacupuncture(**NMOSD**)The efficacy and
mechanism of pain in patients

Project Source: Postgraduate Project

Research Unit: Guangdong Provincial Hospital of
Traditional Chinese Medicine

Head of Research: [name], [name]

Version number:**6.0**

Version date:**2022.03.01**

1. Program summary

Research topic:	To explore the treatment of optic neuromyelitis spectrum disease by electroacupuncture (NMOSD) Study on the efficacy and mechanism of pain in patients
Purpose of the research	Main purpose: to observe the electrical target NMOSD Secondary purpose of the curative effect of patient pain: Discussion NMOSD The mechanism of pain in patients and the mechanism of electroacupuncture in the treatment of pain in patients with optic neuromyelitis spectrum disease
Research hypothesis	Electroacupuncture can be treated effectively. NMOSD Pain in the patient
Research design	Randomized controlled trial
Test group	Electroneedle group
Control group	False needle group
Sample size	20
Selection Criteria	1 Accord with 2021 Diagnostic criteria for optic poliomyelitis genealogical diseases in China's Guidelines for the Diagnosis and Treatment of optic Neurospinal Myelitis Gene Diseases; 2 NRS \geq 4 Score; 3 Patients use stable doses of biotherapy and/or strong loose, before joining the group 30 There is no adjustment plan within the day; 4 Patients before joining the group 30 No standard drug combinations for pain treatment, including antiepileptic drugs, antidepressants or opioids, were adjusted within the day. 5 The patient or the patient's family sign informed consent. 6 18-80 Year-year-old patient.
Exclusion criteria	1 Patients participating in other clinical studies; 2 Patients with low cognitive or mental ability; 3 People who are pregnant, breastfeed or plan to get pregnant during the study; 4 People with serious diseases related to the heart, liver, kidneys or hematopoietic system; 5 Patients with diabetic peripheral neuropathy.
Test cycle	Total test cycle 30 God, all 18 Visit twice a week.
Outcome evaluation indicators	Main indicators: NRS Mark

	Secondary indicators:EDSS、MPQ Rating, SAS Anxiety Scale, SDS Depression Scale, SF-36 Quality of life scale, IL6、TNF-A、fMRI Target
Safety evaluation indicators	Adverse reactions, blood routine, biochemistry, liver function

2. Research background

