6.1 Estimate of sample size

The spectrum disease of optic neuromyelitis is a rare disease, and this study is an exploratory study. Referring to previous studies, the sample size of this topic is 20 Example.

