6.2 Random grouping method

Use a simple randomization method to input the estimated sample content. SPSS V.25.0 Statistical software to obtain order numbers, random seed numbers and grouping results. Then make a random card and seal it in an opaque envelope. Before preparing to start the clinical trial, the serial number will be used according to the order in which the subjects were included in the study, the order number on the corresponding envelope will be opened, and then grouped according to the prompts on the random card. The whole process ensures randomness and secrecy and reduces the bias of researchers.

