[figure not shown]
9. Outcome evaluation indicators

Main evaluation indicators: NRS

Pain sheet rating

Secondary evaluation indicators: EDSS、MPQ Rating, SAS Anxiety Scale, SDS Depression Scale, SF-36 Quality of life scale, IL6、TNF- α 、fMRI Indicators.

10. Technology roadmap

11.2.1 Common adverse acupuncture events/Reaction and treatment: Acupuncture has adverse reactions such as hematoma, stagnation needle, halo needle, etc.

1) Spend money/Hematoma: During acupuncture and acupuncture, local bleeding caused by puncture of blood vessels./Hematoma. Mild bleeding/Of Patients with hematoma can use disinfectant cotton swabs or cotton balls for local compression to stop the bleeding without special treatment. Moderate and severe bleeding/Patients with hematoma should be based on their bleeding./Take corresponding measures to the degree of hematoma, first stop the bleeding to prevent the increase of local swelling, carry out local anti-inflammatory treatment, and ask a surgeon to assist in dealing with it.

2) Stagnation needle: When acupuncture the stagnation needle, you should first relax the local tense muscles, and gently take the needle. Do not pull it hard. It can be opened next to the stagnant needle. 2 Enter the needle inch by inch, and then take out the stranded acupuncture needle. Severe needle stagnation should be assisted by a surgeon.

3) Needle halo: When the patient pricks the needle with acupuncture, he should quickly take out the needle and let the patient lie flat, lower his head, cushion his footsteps, and moxibustion his Baihui acupuncture point. After the patient's halo needle situation is slightly relieved, he can be ordered to drink a little warm boiled water. If the patient's needle is serious and he or she can't wake up, it should be treated according to syncope.

4) Infection: When there is redness, swelling and heat pain in the acupuncture area, the patient's affected part is told to rest and move less to reduce the spread of pain and inflammation, raise the limbs, promote reflux, reduce swelling, do not squeeze the affected part, and carry out local anti-inflammatory treatment. If necessary, you should ask a surgeon to assist in dealing with it.

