11.3.2 Report of serious adverse events

When there is a serious adverse reaction, it should be reported to Guangzhou University of Traditional Chinese Medicine within 24 hours of the second affiliated hospital and fill in the form of serious adverse events.

12. Data management and statistical analysis

Measurement data use: average \pm Standard deviation, median (M), maximum value, Minimum value, matching is used for comparison in the counting data group. T Test (Or pairing symbol rank sum test), variance analysis is used for inter-group comparison (non-normal distribution and variance irregularity are tested by rank sum (Kruskal-Wallis)) and two comparison and calculation 95% CI. The quantitative main outcome indicators of multiple observation time points are analyzed by repeated measurement. Rank sum test is used for comparison between hierarchical data groups (Kruskal-Wallis). The counting data is expressed by composition ratio and rate, and the comparison of total efficiency groups is expressed by cal-square test (or Fisher Accurate probability method). Intergroup composition Compared with comparison 2 \times C Table or 3 \times C Table cal-square inspection.

13. Confidentiality

The results of the research through this project may be published in medical journals, but we will keep the patient's information confidential in accordance with the requirements of the law. Unless required by relevant laws, the patient's personal information will not be disclosed. If necessary, government administrations and hospital ethics committees and their relevant personnel can consult patients' information as required.

14. Ethical standards

The program of this experiment, Case report form, The informed consent form should be approved in writing by the Ethics Committee of Guangdong Provincial Hospital of Traditional Chinese Medicine before it can be carried out.

The researcher or person authorized by the researcher will be responsible for explaining the benefits and risks of participating in the trial to each patient, the legal representative of the patient or notary witness, and shall obtain the patient's written informed consent during the screening examination.

All original informed consent co-signed and signed by the subjects or their legal representatives and the person presiding over the PIC process shall be kept by the researcher.

15. Study schedules

Starting and ending date	Main research content	Expected results

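### Section 12 plans a group test of total efficiency, an outcome that neither outcome list contains and that no section defines, which leaves open a second efficacy test with a threshold that could be chosen after the data

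*Protocol*

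**What the plan says.** Section 12 sets out tests by type of data. For rates it says that "the comparison of total efficiency groups is expressed by cal-square test", and gives Fisher's exact method in brackets as the alternative without saying when it applies. In translation, total efficiency most naturally means a total effective rate, that is, the share of patients judged to have responded.

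The outcome lists do not contain it. Section 1 has "Main indicators: NRS Mark" and Section 9 has "Main evaluation indicators: NRS". The secondary list in Section 9, which opens "Secondary evaluation indicators: EDSS", goes on to MPQ, SAS, SDS, SF-36, IL6, TNF-α and fMRI. Section 1 gives the same secondary outcomes.

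The only NRS threshold in the protocol is the entry criterion of at least 4 (Section 5.1). Section 12 also says that quantitative main outcomes observed at several time points are analysed by repeated measures, so the NRS score has its own planned analysis.

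**The concern.** A protocol may leave the definition of a listed outcome to a later document. Here the analysis section commits to an efficacy comparison of something that the outcome sections do not list at all. A reader cannot tell whether it is a secondary outcome, a version of the primary outcome or a leftover phrase.

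Two things are at stake. First, a response rate without a fixed threshold offers a second route to a claim that electroacupuncture works, and the threshold could be picked to suit the data. Second, if the rate is a dichotomised NRS, it is a less informative analysis of data that are already analysed as a score. That matters with 20 patients.

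**Working it through.** **1. Is the outcome listed or defined?**

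| Item | Sections 1 and 9 | Section 12 |
|---|---|---|
| NRS score | main outcome | repeated measures |
| Total efficiency | absent | chi-square or Fisher |
| Scale, time point and cut-off of total efficiency | absent | absent |

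This step needs no assumptions.

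**2. Inputs for the arithmetic.** The protocol gives a total of 20 ("Referring to previous studies, the sample size of this topic is 20 Example") and no effect size, SD, power or dropout, so it has no power figure to reproduce. Section 6.2 states no allocation ratio ("Use a simple randomization method to input the estimated sample content"). Assumed here: 10 per arm; two-sided 0.05, in line with "two comparison and calculation 95% CI"; a rate derived from NRS; and standardised differences d from 0.8 to 2.0.

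**3. False positives when the cut-off is chosen afterwards.** Trials with no treatment effect were simulated. Each was scored at five cut-offs (a drop of 1 point, a drop of 2 points, a 30% drop, a 50% drop, final NRS below 4), and the smallest p-value was kept. The ranges are over several assumed NRS distributions.

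| Test | Single cut-off | Best of five |
|---|---|---|
| Uncorrected chi-square | at most 4.0–4.5% | 11.1–12.9% |
| Fisher | about 1.3% | 3.6–4.4% |

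A run with every input stated agrees. It used 40,000 trials per setting, entry scores 4, 5, 6, 7 and 8 with probabilities 25, 25, 20, 20 and 10%, a mean drop of 1 to 2 points, SD 1.5 to 2, and rounding to whole scores. Best of five was 11.6–12.0% with chi-square and 3.9–4.1% with Fisher.

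The result depends on the number of cut-offs tried. With percentage change only (mean 20, 30 or 40, SD 30), the best of four cut-offs (25, 30, 50, 75%) gives 7–9% with chi-square and 2.3–3.0% with Fisher. The best of seven gives 11–14% and 3.4–4.5%.

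**4. Which test would be used?** With r responders among 20 and 10 per arm, the expected counts are r/2 and (20 − r)/2. Both reach 5 only if r = 10. Under the common rule of switching to Fisher when an expected count is below 5 (not stated in the protocol), chi-square would almost never apply, and best-of-five error is 3.8–4.4%. The two tests can disagree. For 7/10 against 2/10, chi-square = 20 × (7×8 − 3×2)² / (10×10×9×11) = 50,000/9,900 = 5.05, p = 0.025. Fisher gives p = 0.070.

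**5. Power of the score and of the rate.** For the score, power comes from the noncentral t with 18 degrees of freedom and noncentrality d√(10/2). At d = 1.325 this is 1.325 × 2.236 = 2.96, and power is 80%. For the rate, a normal change is cut so that sham response is 10, 20, 30 or 50%, or at the midpoint between the arms, and both binomials are enumerated. At the midpoint the response rates are Φ(0.6625) = 0.75 and 0.25, which gives 41% (Fisher) and 60% (chi-square).

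| d | NRS score (t test) | Rate, Fisher | Rate, chi-square |
|---|---|---|---|
| 0.8 | 40% | 7–13% | 16–26% |
| 1.0 | 56% | 14–22% | 27–39% |
| 1.325 | 80% | 31–41% | 49–60% |
| 1.5 | 89% | 38–52% | 57–71% |
| 2.0 | 99% | 53–80% | 73–92% |

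The t test stands in for the planned repeated-measures analysis, which is not specified closely enough to compute.

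**The case against.** Section 12 reads like a generic list of tests by data type. It also offers Kruskal-Wallis and tables for three groups in a two-arm trial, so total efficiency may be a template phrase, and nothing in the protocol says that a conclusion will rest on it. A statistical analysis plan, not shown here, may define it. This lowers the severity and means that the missing cut-off alone would be no finding. It does not remove the disagreement between Section 12 and the outcome lists, which stays in the protocol whatever a later document adds.

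A reader might infer that the trial's efficacy analysis loses half its power. The protocol does not support that. The NRS score keeps its own repeated-measures analysis, and the protocol never says that the rate comes from NRS. The loss is also not a fixed half. For d from 0.8 to 1.5 the rate keeps about 17–59% of the score's power with Fisher and 41–80% with chi-square.

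A reader might also combine the 11–13% error with the 41% power. They belong to different tests. Chi-square pairs about 11–13% error with 60% power, and Fisher pairs about 4% with 41%. With Fisher, even the best of five cut-offs stays below 5%, though that is roughly three times the rate for one fixed cut-off.

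**Conclusion.** The point holds as an internal inconsistency: Section 12 tests an outcome that Sections 1 and 9 do not list and that no section defines. This rests on the text alone.

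The numerical consequences are conditional on an NRS-derived rate, 10 per arm, two-sided 0.05, and the assumed distributions, cut-offs and effect sizes. On those terms a free threshold pushes error clearly above 5% only if uncorrected chi-square is used throughout. The dichotomised test is weaker than the score under either test at every effect examined. The primary NRS analysis is unaffected unless the rate is used in its place.

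The severity is minor. Section 6.1 says that "this study is an exploratory study", and the main outcome is named consistently.

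**What to change.** Delete the total-efficiency comparison from Section 12. State that the efficacy conclusion rests on the between-group difference in NRS score, adjusted for baseline NRS, with its 95% CI. Section 8 already collects NRS at screening, and the baseline can enter the planned repeated-measures analysis as a covariate, so no new data are needed.

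If a response rate is wanted, add it to Section 9 (and to the summary in Section 1) as supportive only. Give its scale, its time point and a single cut-off fixed before unblinding, and name Fisher's exact test as the only test. Fisher has less power than chi-square here, which is acceptable for a supportive outcome.

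The cost is one clause removed or one outcome line added. The downside is that a familiar effective rate is lost or becomes supportive.
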